**REGULATORY FRAMEWORK:**

Please indicate all that apply:

	DOD (Department of Defense)
	DOE (Department of Energy)
	DOJ (Department of Justice)
	ED (Department of Education)
	EPA (Environmental Protection Agency)
	FDA (Food and Drug Administration)
	HHS (Department of Health and Human Services)
	VA
	Other:

Is this a clinical trial under ICH-GCP E6?  Yes  No

If yes, please confirm that the research team is familiar with and agrees to comply with the investigator requirements cited in ICH-GCP E6.  Yes  No

ICH-GCP E6 can be accessed by copying and pasting this URL into your browser: <http://www.fda.gov/downloads/Drugs/Guidances/ucm073122.pdf>

**FUNDING:**

Indicate if the protocol is funded. If so, provide sponsor and SPO Click ERA record number. This protocol is not funded. It is part of the CTSC RFA for "Linking Clinical Trials to Drug Discovery and Repurposing Award".

## 1. Objectives

1.1. The long-term goal of this proposal is to identify non-opioid drugs that harness endogenous anti-inflammatory mechanisms resulting in the suppression of proinflammatory cytokines such as IL-1 $\beta$ , providing a novel approach to treat chronic pain in people while lacking potential for addictive side effects.

Specific Aim I: pramipexole blocks the activation of NLRP3 and consequent production and release of the proinflammatory cytokines IL-1 $\beta$ , IL-6 and TNF- $\alpha$ , and increases production of the anti-inflammatory cytokine interleukin-10 (IL-10).

The goal of Aim I (Phase I) experiments is to examine the specific anti-inflammatory mechanisms of pramipexole on PAMP, DAMP and opioid stimulated immune cells, THP-1 cells will be used.

Specific Aim II: pramipexole treatment will provide therapeutic benefit to patients experiencing suboptimal pain relief from current standard therapy with concurrent reduction of TLR4-NLRP3-cytokine expression in peripheral blood mononuclear cells.

The goal of Aim II (Phase II) will be to determine the therapeutic benefit of pramipexole for pain, which is a repurposing of this FDA-approved drug with a good safety profile.

1.2. Our overarching hypothesis is that pramipexole will control clinical pain by suppressing the activation of the TLR4-NLRP3-IL-1 $\beta$  pathway and prevent IL-1 $\beta$  release from peripheral immune cells. These findings have provided the current impetus to examine pain therapeutic drugs targeting immune-related factors either upstream or downstream of IL-1 $\beta$  signaling.

## 2. Background

### 2.1.

[figure not shown]
The rate of US opioid-related overdose deaths from 2013 - 2016 increased by an astonishing 88% per year, while overdose deaths due to other drugs remained virtually unchanged [1, 2]. These increasing opioid-related death rates are linked to increases in prescription opioid misuse (medical and non-medical) as well as illicit opioid use (heroin) [3, 4]. Despite medical prescription opioid misuse generally declining during recent years [5, 6], the number of individuals who misuse prescription and illicit opioids continues to increase [7, 8]. These data reveal an emerging opioid misuse epidemic (medical, non-medical, and illicit) [5, 9-13]. Recent data reveal the discrete geographical regions where states have been hardest hit by this growing epidemic [3]. Indeed, data analyzed from just 2014 alone reflect New Mexico had undergone the greatest opioid-related overdose death rate relative to other Mountain states, the Pacific and the Western south-central state regions [14]. These statistics reflect an unprecedented public health crisis of prescription opioid and heroin abuse both regionally and nationally. While the underlying causes related to this public health crisis are largely speculative, one possible contributing factor is the dramatic escalation of prescription opioid treatment for chronic pain over the past decade [15].

The escalation of opioid treatment is particularly disconcerting because preclinical studies convincingly support that not only do opioids exert negative consequences for

pain [16-19], but also that chronic pain can be targeted by non-opioid drugs that lack direct actions on neurons thereby reducing addiction liability [20, 21]. In point of fact, a large number of reports using animal models reveal that trafficking immune cells to the central nervous system (CNS) and immune-like glial cells within the CNS (e.g. astrocytes and microglia) are necessary for the development and maintenance of acute-to-chronic pain problems [22-24]. Notably, experimental chronic pain that is induced by a variety of manipulations modeling different etiologies of clinical pain is mediated by peripheral immune cell and CNS-derived proinflammatory cytokines that act to exacerbate pain signals. The most widely studied immune and glial cell factor is the proinflammatory cytokine, interleukin-IL-1 $\beta$  (IL-1 $\beta$ ). This cytokine, considered a “gatekeeper of inflammation and neuroexcitatory events”, is necessary and sufficient for mediating the transmission of pathological chronic pain. Evidence from preclinical and clinical studies shows that blocking immune and/or glial IL-1 $\beta$  production and/or its action suppresses chronic pain [21].

The discovery that cytokines like IL-1 $\beta$  as well as others including tumor necrosis factor-alpha (TNF- $\alpha$ ) were critical for mediating pathological chronic pain was significant because these immune-derived signaling molecules have been known for decades to play essential roles in mounting an innate immune response (e.g. myeloid-derived cells such as macrophage but not T or B cells) including leukocyte migration to tissue damaged sites and fever. Indeed, IL-1 $\beta$  was originally identified as a pyrogenic factor stimulated by pathogen invasion such as bacteria; gram negative bacterial cell wall particles such as lipopolysaccharide (LPS). LPS is a widely-used immune activator to experimentally mimic pathogen invasion and induces macrophage release of IL-1 $\beta$  and TNF- $\alpha$  [25]. LPS mimics pathogen invasion via receptor recognition of pathogen associated molecular pattern (**PAMPs**). LPS delivered spinally in experimental mice develop pain that is now thought to occur via IL-1 $\beta$  release [26]. In other words, the pain system is capable of harnessing ancient molecular pathways of the innate immune system for the purpose of facilitating host survival and wound healing (triggering the disuse of the injured tissue). The cytokine release from immune and glial cells is triggered upon factors released from stress/damaged cells, now characterized as danger-associated molecular patterns (**DAMPs**) that bind discrete immune receptors (discussed below). Recognition of DAMPs allow cells to distinguish between non-injured vs. injured self [27]. Therefore, when conditions become pathological, adverse sterile neuroimmune stimulation drives acute-to-chronic pain states via DAMP stimulation.

**Figure 1** is a schematic that represents the factors that stimulate and are induced within the classic immune pathway that ultimately lead to the release of proinflammatory

cytokines like IL-1 $\beta$ .

However, even more intriguing is the mounting evidence that repeated opioid exposure/treatment results in significant negative consequences for pain [16, 20, 28, 29]. Preclinical studies of the past few years show opioid drugs activate the same innate immune proinflammatory pathways necessary for the production and release of IL-1 $\beta$  in both peripheral immune and glial cells [29-32] (see **Figure 1**). The action of opioids on immune and glial cells was discovered to occur through the non-classical opioid receptor, toll-like receptor 4 (TLR4) [32-35]. TLR4 activation triggers the active formation of the intracellular NOD-like receptor protein 3 (NLRP3) inflammasome, a protein complex necessary for the ultimate production of IL-1 $\beta$  [36, 37]. Thus, the activation of TLR4 on immune cells and glia by opioids may underlie the reported observation that chronic opioids paradoxically induce pain (e.g. opioid induced hyperalgesia) [38, 39]. It therefore follows that neuropathic pain is exacerbated and prolonged by opioid repeated/chronic treatment [16, 28, 29]. In addition, recycling of opioid receptor upon activation by opiate drugs (e.g. morphine) is profoundly distorted in neurons such that the intracellular opiate-receptor interaction is substantially prolonged [40]. Taken together, these reports suggest non-opioid compounds may provide substantially better therapeutic benefit than opiate drugs. Therefore, the *long-term goal* of this proposal is to identify non-opioid drugs that harness endogenous anti-inflammatory mechanisms resulting in the suppression of proinflammatory cytokines such as IL-1 $\beta$ , providing a novel approach to treat chronic pain in people while lacking potential for addictive side effects.

[figure not shown]
Pramipexole: FDA approved drugs that demonstrate an excellent safety profile in humans while also demonstrating the above-noted anti-inflammatory profile could be explored as **repurposed drugs for non-opioid pain therapeutics**. One such compound that satisfies this profile is pramipexole, which is now documented to reduce inflammation in several preclinical animal models of peripheral inflammatory pain [41]. While this study did not examine rodent pain behaviors, the classic hallmarks of hindpaw edema and neutrophil accumulation were assessed, with pramipexole significantly blunting these inflammatory processes. In a separate study examining brain inflammatory cytokines in mice following low-dose LPS inflammation, IL-1 $\square$  mRNA levels were blunted following treatment with pramipexole [42]. Pramipexole is well-documented as a preferred dopamine-2/3 (D2/D3) receptor agonist that is FDA approved for alleviating movement disorders in Parkinson Disease and for treating restless leg syndrome, with modest therapeutic outcomes [43-48]. Therefore, based on the documented safety profile of pramipexole, we propose to explore whether it exerts anti-inflammatory (anti- IL-1beta actions) resulting in therapeutic pain suppression in people.

## 2.2. Preliminary data.

All experiments in this phase will be performed at the Center for Molecular Discovery ([name], co-I and Director of this core) using the human monocytic leukemia cell line, THP-1. This cell line is routinely used in the core facility to examine drug effects on the TLR4-NLRP3-IL-1 $\beta$  pathway by quantifying dose-dependent effects on IL-1 $\beta$  protein release. Upon stimulation by LPS, these cells can provide a reliable indication of specific TLR4-NLRP3 activation as measured by the production of the adaptor protein apoptosis-associated speck-like protein (ASC) and IL-1 $\beta$  release [49]. Additionally, THP-1 cells activate upon adenosine triphosphate (ATP), which signal to cells as a DAMP [28, 49].

It is important to note that following TLR4 activation by PAMPs, DAMPs or opioids, subsequent phosphorylation of protein kinases p-p38 and p65 and nuclear factor kB (NFkB), generates NLRP3 inflammasome complex formation required for IL-1 $\beta$  transcription and production [50].

[figure not shown]
**Figure 2** demonstrates the feasibility of utilizing THP-1 (human myeloid cells) upon stimulation as a cellular screen to examine the suppression of cellular activation, as measured by a reduction in IL-1 $\beta$  following drug application. Other reports show that following LPS stimulation, Alprostadil, also known as prostaglandin E1 (PGE1), reduces NF-KB activity and spinal proinflammatory cytokine IL-1 $\beta$  and TNF $\alpha$  production [51, 52]. In the current pilot data provided [name] (co-Investigator), THP-1 stimulated cells with LPS reveal an Alprostadil dose-dependent reduction in IL-1 $\beta$ . Conversely, examination of Resveratrol, a drug that is characterized to act at the integrin  $\alpha$ V $\beta$  receptor to induce phagocytosis [53], generates a distinctly different profile of IL-1 $\beta$  release from THP-1 cells. While Resveratrol is characterized to induce the anti-inflammatory related nuclear receptor, peroxisome proliferator-activated receptor gamma (PPAR $\gamma$ ) [54], increased IL-1 $\beta$  is observed above levels induced by LPS stimulation (red triangle) suggesting higher doses may be inducing general increases in transcriptional activity, a known function of PPAR $\gamma$ . As such, the pattern of THP1 activation in response to drug in the presence of stimulation can be used to indicate pramipexole-dependent actions in reducing the TLR4-NLRP3- IL-1 $\beta$  inflammatory pathway. As depicted in Figure 1, PAMPs and DAMPS can be applied to stimulate TLR4-NLRP3. Therefore, LPS and the DAMP, high mobility group box 1 (HMGB1) will be used to stimulate THP-1 cells. HMGB1 is relevant to the proposed study because it is released from damaged nerve terminals in the spinal

cord and characterized to mediate persistent pain [55].

**Figure 3:** Based on evidence demonstrating general anti-inflammatory effects of pramipexole (reduced IL-1 $\beta$  production, neutrophil accumulation and edema formation), a pilot study was performed in mice to examine the effects of an intravenous injection of pramipexole on pathological light touch sensitivity in a model of peripheral sciatic neuropathy. A widely-used and well-characterized rodent model of peripheral neuropathy was applied by loose ligation of 3 chromic gut sutures around one sciatic nerve (chronic constriction injury; CCI) that leads to hindpaw sensitivity to light touch, clinically referred to as allodynia. Allodynia is a hallmark of pathological sensory processing and is frequently a problem in pain patients. In this figure, compared to sham (no surgery) controls with vehicle or pramipexole treatment, mice with CCI and i.v.

vehicle/placebo treatment reveal stable allodynia (light touch responses from 0.023 – 0.068 g) throughout the timecourse (white squares). Conversely, those mice with CCI followed by i.v. pramipexole reveal a profound reversal from allodynia (0.5 or 5.0 ug; blue or red triangle, respectively) with allodynia returning by 24 hrs after drug injection in keeping with the reported half-life of pramipexole [43, 48]. These data support the exploration of pramipexole as a possible inhibitor of the TLR4-NLRP3-IL-1 $\beta$  pathway, and as such, a possible chronic pain therapeutic that is already FDA-approved for the treatment of other clinical conditions (explored in **Phase II** of the current proposal).

### 2.3. Additional Background and Rationale

[figure not shown]
A growing body of evidence supports that repeated opioid exposure triggers TLR4-NLRP3-IL-1 $\beta$  activation and release, which may underlie the development of opioid-induced prolongation of pain and hyperalgesia [16, 28, 29, 39]. THP1 cells are characterized to respond to opioid stimulation by potentiating NF $\kappa$ B [56], and naloxone, a known antagonist at the mu opioid receptor, also blocks TLR4 activation [17, 33-35]. Indeed, naloxone prevents LPS-induced NLRP3 complex formation (NLRP3 + ASC) in THP-1 cells [49]. Results from these experiments could lead to (a) further support that pramipexole is a viable alternative to opioid as a pain therapeutic, and/or (b) co-administration of opioid compounds with pramipexole. The implications are far reaching. To capture TLR4 immune cell activation by distinct mechanisms, PAMPs, DAMPs or opioids, THP-1 cells will be stimulated with either LPS, HMGB1 (a DAMP) or an opioid compound (either beta-endorphins or morphine). Increasing doses of pramipexole will be given, and levels of IL-1 $\beta$  will be analyzed. In addition, cell supernatant and lysates will

be collected to evaluate protein and mRNA for TLR4, p38, NFkB, NLRP3, Caspase-1, which is an enzyme activated only after NLRP3 complex formation with ASC that is required for mature IL-1 $\beta$  release, as well as the proinflammatory cytokines, IL-1 $\beta$ , TNF- $\alpha$  and HMGB1, and IL-10

### **3. Study Design**

3.1. This is a proof-of-concept randomized placebo-controlled clinical trial.

**Figure 4: Study Design**

3.2. Describe blinding, if applicable.

All subjects will pick up the allotted capsules from the UNMH Clinical Pharmacy that will dispense either pramipexole or placebo. A randomization table will determine which subject will receive pramipexole or placebo.

### **4. Inclusion and Exclusion Criteria**

#### 4.1. Recruitment of Subjects and Inclusion

Subjects who qualify for inclusion will be those potential subjects identified by [name] being seen at the UNM Pain Clinic who are experiencing pain with "suboptimal" pain relief (defined as discussed below in this section) by standard pain treatment. A randomization table for all subjects receiving pramipexole vs. placebo will be generated such that the Clinical Research Coordinator will use as a template when dispensing drug at the time of consent. All types of chronic pain will be considered, and thus, specific types of chronic pain will not be part of the inclusion or exclusion criteria. Non-English, Spanish speaking subjects will be included. Adults 18 yrs. or older will be included. Women who are not post-menopausal or have not undergone an oophorectomy/hysterectomy will be excluded.

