### **5. Number of Subjects**

- 5.4. All subjects will be recruited from the UNMH outpatient population from the UNMH Pain Center.
- 5.5. The target sample size is 30 subjects with complete data. The investigators may recruit up to 45 patients to allow for any dropouts.
- 5.6. All subject recruited will participate. There will be no screening after recruitment.

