## **7. Study Endpoints**

- 7.4. The primary endpoint is the paper-and-pencil survey, the Brief Pain Inventory. The secondary study endpoints will be mRNA and protein analysis from blood samples provided at the initiation and terminal of the study.
- 7.5. *Safety endpoints of the study will include the following: (1) Worsening of pain score or increased verbal dissatisfaction with pain relief, (2) sudden onset of sleep without warning, (3) intense urges, (4) hallucinations and/or psychotic-like behaviors, (5) fever, and (6) orthostatic hypotension. While the patients who experience these adverse events, dosing with pramipexole will require a 50% step-wise reduction over a period of two weeks. Given the maximal allowable dose is 0.75 mg, this prescribed step-wise reduction is well within the manufacturer's recommended tapering of pramipexole, which the recommended dose reduction is 0.375 per day.*
- 7.6. No exploratory endpoint are in the current study.

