## **9. Resources Available**

- 9.4. The PI and study staff have received training for clinical trials. [name] (PhD) is a basic scientist conducting the cell assays and interpreting the data results. [name](PhD) is a basic scientist directing the CTSC core for conducting the cell assays and interpreting the resultant data. [name] (PhD) is a statistician and familiar with clinical trials designs, and [name] (MD) is a physician who specialized in pain treatment at the UNMH Pain Clinic.
- 9.5. [name], MD will be responsible for medical decision-making and ordering and evaluation of necessary diagnostics and therapeutics.
- 9.6. [name] treats 15-30 patients daily at the UNMH Pain Clinic. With this high access to patients, the goal of enrolling 30 patients during an 11 month period is predicted to be very feasible.

All 30 recruited patients will be needed with no further screening.

An estimated 6 hrs per patient will be devoted to consent, completing surveys, blood draw, scheduling and dispensing the pramipexole or placebo by the Clinical Research Coordinator.

- The facilities used will be at the CTSC where consent, enrollment, scheduling visits, obtaining blood samples, completion of the Brief Pain Inventory survey, dispensing drugs at initiation and at midterm (end of week 2,) and collecting unused drug at termination. For the biological assays from human cell lines or from blood samples, the clinical laboratory arm of the CTSC, Center for Molecular Drug Discovery, will be used.
- The availability of medical and/or psychological resources that subjects might need as a result of an anticipated consequences of the human research will be available by [name] or by referral from [name]. The anticipated consequences of the research will be (1) improved pain relief, (2) no change in pain relief, or (3) a worsening of pain. [name] will continue to monitor patients after the study is terminated, as these patients will continue to receive outpatient care from the pain clinic.

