- All persons assisting with the research will have group meetings once every 3 months in the conference room in the Dept of Anesthesiology. Goals of each meeting will include research progress updates, preliminary findings of the pain scores derived from the Brief Pain Inventory, problems or unanticipated adverse events, how these adverse events were managed, and action items for continued progress or needed to adjust to potential changes. [name] will provide updates on his clinical observations from his pain patients, [name] will provide updates with regard to progress or impediments of cell assays, [name] will provide a summary of data collected from the cell based assay from Phase I (Specific Aim I) and [name] will provide input for preparation of appropriate statistical analysis, manuscript preparation and future NIH NIDA grant preparation should the data support the research hypothesis.
- If CTSC resources are being accessed, the signed CTSC resources attachment must be uploaded on the CTSC Submission page in Click.

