## **12. Study Procedures**

The goal of Phase II will be to determine the therapeutic benefit of pramipexole for pain, which is a repurposing of this FDA-approved drug with a good safety profile. In collaboration with [name] (co-I at UNMH Pain Clinic), patients from the UNM pain clinic will be recruited who are experiencing modest or suboptimal pain relief. The patient will meet the CTSC Clinical Research Coordinator, who will escort the patient to the Clinical Research Lab. At the time, an explanation of the study, consent, the Brief Pain Inventory survey will be completed, blood draw and Clinocard will be given to the patient (\$15/visit). Scheduling for the midterm visit to the CTSC (at the end of two weeks) will be determined. At the time of consent, all patients will be under standard pain treatment and will be randomized into two groups: (1) patients receiving pramipexole in addition to their standard ongoing pain treatment, or (2) no pramipexole but will continue to receive the standard pain treatment. Patients will be followed up in the morning at weekly intervals to provide pain scores either by phone (for week 1 and 3), or by return visit (for end of week 2 and at the end of week 4) until study termination which is at the end of week 4.. At the initiation of the study and at the end of 4 weeks, blood will be collected and analyzed for mRNA for TLR4, p38, NFKB, NLRP3-ASC, Caspase-1, IL-1 $\beta$ , TNF- $\alpha$ , HMGB1, and IL-10. The dose and route of administration of pramipexole will be identical to that previously approved for the treatment of Restless Legs Syndrome and according to manufacturer's recommended prescribing protocol (Mirapex, Boehringer Ingelheim Int. GmbH). Briefly, oral dosage will be titrated each week to achieve a weekly total daily dose of 0.125 (mg), 0.250, 0.5 or 0.750. Patients will take one capsule containing pramipexole or placebo 2-3 hours before bedtime.

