Patient recruitment, assessment of Brief Pain Inventory (BPI): Pain scores and blood draws will be conducted at the CTSC Participant Clinical Interactions Unit with the CTSC Clinical Research Coordinator. Blood samples collected by the CTSC Clinical Research Coordinator will be analyzed at the Center for Molecular Discovery by personnel from [name] lab, trained by personnel from the Center for Molecular Drug Discovery (Director; [name], co-I). Personnel from the [name] lab have expertise in inflammatory marker analysis from PBMCs [57, 58]. All freshly collected blood samples will be frozen and stored by the Clinical Research Coordinator at the CTSC Clinical Laboratory and will be transported to the Center for Molecular Drug Discovery once ALL of the samples for the study (all 30 patients) have been collected. This is to allow for assay to be conducted at the same time to avoid potential effect of 'time of assay' that may impact data.

All subjects will therefore meet with the CTSC Clinical Research Coordinator for a total of 3 times; at the initiation of the study, at mid-term when the second batch of drug is dispensed and unused drug is returned, and at termination for a second and final blood draw and providing all completed Brief Pain Inventory surveys (5/patient). At the termination of the study, patients will turn in their paper copies of the Brief Pain Inventory questionnaire completed for each week of the study (total 4 weeks). Original data records are important to demonstrate all necessary physical documentation of the study.

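### The protocol conflicts on who dispenses and who uses the randomization table; if the coordinator text is followed with an uncoded table, the person who takes consent and collects pain scores can know the arm

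*Combined protocol and SAP*

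**What the plan says.** Section numbers below follow the headings in the body of the protocol.

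**Coordinator account.** Section 4.1 states: "A randomization table for all subjects receiving pramipexole vs. placebo will be generated such that the Clinical Research Coordinator will use as a template". Its stated use is for giving out drug as consent is taken. The sentence recurs in Section 14 (Adequacy of Protection Against Risks) and Section 19. Section 9 includes in the coordinator's hours per patient "scheduling and dispensing the pramipexole or placebo by the Clinical Research Coordinator".

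**Pharmacy account.** Section 3.2, the item on blinding, has all patients collect their "capsules from the UNMH Clinical Pharmacy that will dispense either pramipexole or placebo". Section 31 also has the research pharmacy dispense, guided by a randomization table, without naming who uses it. In Section 13, item 3 of the compounding procedure ties dispensing to the pharmacy's hours and staff.

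**The coordinator's other tasks.** The coordinator obtains consent (Section 24), collects the BPI (Sections 8 and 14) and records all adverse events (Section 14). Section 7 says: "The primary endpoint is the paper-and-pencil survey, the Brief Pain Inventory".

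**Blinding.** In Section 13, item 2 of the compounding procedure makes active and placebo capsules look the same at each dose level. Section 3.2 names no blinded role. Section 3.1 calls the trial randomized and placebo-controlled only. The one mention of double-blinding, in Section 14, describes earlier Parkinson's disease trials.

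**The concern.** A table that lists pramipexole or placebo by patient is the allocation code. Whoever dispenses from it can see the next assignment before a patient has agreed to join, and each current assignment for as long as the patient is in the study. Under the coordinator account, that person also holds the consent discussion, takes the pain scores and writes down the adverse events.

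The endpoint is a subjective score. Knowledge of the arm could affect how and when consent is sought, how scores are elicited by phone, which complaints are recorded and how they are described. Staff who follow Section 4.1 and staff who follow Section 3.2 would handle the code differently. Concealment that is lost during enrolment cannot be restored afterwards.

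**Working it through.** No figure in the plan bears on this, so the check sets the texts side by side.

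| Question | Coordinator account | Pharmacy account |
|---|---|---|
| Who dispenses? | Coordinator: 4.1, 14, 19 (one sentence, three places) and 9 | Pharmacy: 3.2, 13 (item 3), 31 |
| Who uses the table? | Coordinator: 4.1, 14, 19 | Section 31 links the table to pharmacy dispensing but names no user; 3.2 mentions a table and no user |
| Where is drug obtained? | At the clinical research unit, at enrolment and mid-term: 9 | From the pharmacy: 3.2 |
| Is the table coded? | Not stated | Not stated |

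**Step 1: is the conflict explicit?** On dispensing, yes. On the table it is softer. Three places have the coordinator use it, and no section says who holds it.

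**Step 2: do the roles overlap in time?** Dispensing happens twice, at enrolment and at mid-term (Section 9). At enrolment the coordinator's visit covers consent and the baseline BPI (Section 12). At mid-term the week-2 scores and the second drug supply fall in one coordinator meeting (Section 14). Both of the two dispensing occasions therefore coincide with a BPI collection. At weeks 1 and 3 the coordinator takes scores by phone.

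**Step 3: what could be known?** With an uncoded table, the arm of every patient enrolled: 30 with complete data, up to 45 recruited (Section 5).

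**Step 4: is there another route to arm information?** The interim review in Section 14 follows enrolment of the 15th patient. Its trigger is adverse events of grade 2 or higher in three or more active-arm patients.
- Fewer than 3 affected patients overall: the active arm has at most 2, the trigger cannot be met, and no arm data are needed.
- Exactly 3 affected overall: met means 3 of 3 are on pramipexole, so the answer reveals all three allocations.
- Patients still to enrol after the 15th: 30 − 15 = 15, or up to 45 − 15 = 30.

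The principal investigator and two other investigators conduct this review. The plan does not say who makes the by-arm count or from whom it is kept.

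**The case against.** The strongest reply is that the accounts can be reconciled: the pharmacy compounds, assigns and dispenses, the coordinator only hands over, and the sentence about the template is a drafting slip copied twice. The capsules are matched, which shows an intention to mask. The BPI is completed by patients on paper, and Sections 14 and 20 also mention electronic surveys under a study ID. Phone scores can be compared with the paper originals returned at the end. The physician identifies and screens patients before they meet the coordinator, and Section 5 adds "All subject recruited will participate. There will be no screening after recruitment".

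Much of this stands, and it limits the risk. It does not settle the point. A coordinator who only hands over labelled supplies needs no table of treatments, and no section describes a coded one. Screening by the physician does not cover the consent discussion, and patient-completed forms do not cover adverse-event recording.

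Readers might infer more than the documents support:
- **That the trial is open-label, or that controls get no placebo.** One sentence in each of Sections 12 and 13 describes controls as receiving no pramipexole, but Section 12 also says "Patients will take one capsule containing pramipexole or placebo", and Section 13 describes matched placebo capsules.
- **That no one is blinded.** The opening pages and Figure 4 were not available for this review, so a blinding label there cannot be excluded. Such a label would not by itself settle who uses the table.
- **That the team sees pain scores by arm at its quarterly meetings.** Section 9 lists "preliminary findings of the pain scores derived from the Brief Pain Inventory" as an agenda item and does not say whether they are pooled.
- **That the principal investigator must not see safety data by arm.** That is a debatable trade-off in a trial of this size, and the protocol gives this investigator the safety review.

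**Conclusion.** The concern holds in conditional form. The conflict on who dispenses is explicit, and three places have the coordinator work from a pramipexole-versus-placebo table. If that text is followed and the table is uncoded, allocation concealment and blinded data collection are both compromised for up to 45 patients. That the table is uncoded is an assumption drawn from silence. The documents do not show that the coordinator will in fact know the arm.

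The size of any bias cannot be computed from the documents. Counts of patients or surveys describe exposure, not bias. The missing statement on staff blinding is a finding about the text that could be seen. The interim review is a secondary point: its active-arm trigger can require arm data, and the plan does not say who handles them.

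The conflict should be settled before enrolment, because concealment cannot be repaired later and the correction costs little.

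**What to change.** - **Sections 4.1, 14 and 19:** replace the sentence that has the coordinator use the table. State that the table is held and used only by the investigational pharmacy, which assigns treatment and labels matched capsules with the subject number.
- **Section 9:** correct the dispensing text to match. The coordinator may hand over labelled supplies but does not see the table.
- **Section 3.2:** state that patients, the coordinator, the treating physician and whoever judges whether an adverse event is related to study drug (Section 14) are blinded until database lock. The pharmacy holds the code for individual unblinding.
- **Section 14, interim review (secondary):** state who makes the active-arm count, and keep it from staff who enrol patients or collect BPI scores. The notification threshold stays as it is. Whether the principal investigator sees the by-arm result is for the sponsor to decide and state.

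The cost is minor protocol wording and one pharmacy working instruction. The pharmacy already compounds the matched capsules, and no extra patients or visits are needed.
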